6.4.9 Physical Examinations

Physical examination findings will be presented in by-subject data listings.

6.4.10 Neurological Examinations

Neurological examination findings will be presented in by-subject data listings.

8 APPENDICES

8.1 APPENDIX 1: Partial Date Conventions

ALGORITHM FOR TREATMENT EMERGENCE OF ADVERSE EVENTS:

Incomplete Adverse Event Start Date

If *year* and *day* are present but *month* is missing, assume that only *year* is present in the steps below.

If the start date is completely missing: set the date to the first dose date.

If *year* is present and *month* and *day* are missing:

If *year* = year of first dose: set the date to the first dose date.

If *year* < year of first dose: set *month* and *day* to December 31st.

If *year* > year of first dose: set *month* and *day* to January 1st.

If *month* and *year* are present and *day* is missing:

If *year* = year of first dose, and:

If *month* = month of first dose: set *day* to day of first dose.

If *month* < month of first dose: set *day* to last day of *month*.

If *month* > month of first dose: set *day* to 1st day of *month*.

If *year* < year of first dose: set *day* to last day of month.

If *year* > year of first dose: set *day* to 1st day of month.

Should the imputed start date based on the rules above be after a complete end date, use the end date instead of the date that would otherwise be imputed.

ALGORITHM FOR PRIOR / CONCOMITANT MEDICATIONS:

Incomplete Prior/Concomitant Medication Start Date

If *year* and *day* are present but *month* is missing, assume that only *year* is present in the steps below.

If the start date is completely missing: set the date to the first dose date.

If *year* is present and *month* and *day* are missing:

Set *month* and *day* to January 1st.

If *year* and *month* are present and *day* is missing:

Set *day* to 1st day of the month.

Should the imputed start date based on the rules above be after a complete end date, use the end date instead of the date that would otherwise be imputed.

Incomplete Prior/Concomitant Medication End Date

If *year* and *day* are present but *month* is missing, assume that only *year* is present in the steps below.

If the end date is completely missing and ongoing is checked: set the date to the last dose date.

If the end date is completely missing and ongoing is not checked: do not impute.

If *year* is present and *month* and *day* are missing:

Set *month* and *day* to December 31st.

If *year* and *month* are present and *day* is missing:

Set *day* to last day of the month.

Should any of the imputed end dates come before the start date (either complete or imputed) then use the start date instead.

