6.1.5 Prior and Concomitant Medication

The incidence of concomitant medication use will be summarized by WHO Drug Dictionary (WHODD) anatomic therapeutic chemical (ATC) Level 2 classification (i.e., therapeutic main group) and preferred name. The WHODD version used for reporting will be provided in the relevant table and listing footnotes.

A subject will be counted only once at each level of reporting. Prior medications are those which have been identified to have been discontinued prior to the treatment start date (e.g., taken exclusively during the pre-therapy period). Concomitant therapies are defined as all therapy

ongoing at the time of enrollment and all therapy other than study drug received during the study. Concomitant medication use will be summarized and presented by study part and cohort for the SAF population. Partial start/end dates will be imputed according to Appendix 1 for the determination of concomitance. Medications will be sorted by decreasing frequency of ATC classification based on overall subjects. Preferred drug names will be sorted in descending order by frequency within each ATC classification based on overall subjects.

All prior and concomitant medication data will be listed including the verbatim and preferred drug name and ATC Level 2.

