6.4.1 Adverse Events

An adverse event (AE) is recorded if it is a new event that was not present at Screening, or is the worsening of an event present at Screening. A treatment-emergent adverse event (TEAE) is defined as any AE that starts or worsens after first dose of study drug. Partial start dates will be imputed according to Appendix 1 for the determination of treatment-emergence. Any AEs with missing start time that occur or worsen on study day 1 will be assumed to be treatment-emergent.

AEs will also be assessed for outcome, severity, relationship to study drug, and seriousness. Any missing severity assessments will be assumed to be Grade 3 (severe) and missing relationship assessments will be assumed to be related. Expected AEs related to KNX100 treatment are provided in the KNX100 Investigator's Brochure. Adverse events will be coded based on the MedDRA for reporting by SOC and PT. SOC's will be ordered in accordance with the international agreed upon sort order for SOC followed by descending order of overall incidence. The MedDRA version used for reporting will be described in the relevant table and listing footnotes.

An overview of TEAEs will be produced, including counts and percentages of subjects as well as number of events by study part and cohort with any incidences of: TEAEs, TEAEs grade 3 or higher, TESAEs, TEAEs related to study treatment, and TESAEs related to study treatment.

Summaries of adverse events by SOC and PT will present the number and percentage of total subjects and number of events (where noted below) by study part and cohort and will include the following types:

- TEAEs (including number of events)

- TEAEs by maximum severity
- TEAEs by highest relationship to study treatment
- Treatment-emergent SAEs

When calculating the incidence of AEs, each AE will be counted only once for a given subject within a MedDRA category (e.g., overall, system organ class, or preferred term), but all occurrences of the same event will be counted in the number of events. When AEs are summarized within levels of another AE assessment (e.g., relatedness or severity), AEs will be counted once per subject at the worst/highest level of the assessment (e.g., highest relationship to study drug or greatest severity).

A comprehensive listing of all adverse events will be provided in a by-subject data listing. In addition, a listing of all treatment-emergent SAEs will be provided.

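### SAP Appendix 1 lets only a complete end date override an imputed start date, so certain doubly incomplete records that ended before dosing are flagged treatment-emergent or concomitant

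*SAP*

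**What the plan says.** The rules are in SAP Appendix 1 (8.1). SAP 5.3 restricts their use to setting the treatment-emergent and concomitant flags.

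**Start dates.** Both algorithms share one rule: "If the start date is completely missing: set the date to the first dose date". For adverse events, a start known only as a year equal to the dosing year gets the same treatment: "set the date to the first dose date". Both algorithms then allow one correction: "Should the imputed start date based on the rules above be after a complete end date, use the end date instead". Appendix 1 has no rule for partial adverse event end dates.

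**Medication end dates.** A month-and-year end is completed by "Set *day* to last day of the month", and a year-only end becomes 31 December. The last rule reads "Should any of the imputed end dates come before the start date (either complete or imputed) then use the start date instead".

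**Definitions that use these dates.** SAP 6.4.1 has a TEAE "defined as any AE that starts or worsens after first dose of study drug" and adds: "Any AEs with missing start time that occur or worsen on study day 1 will be assumed to be treatment-emergent". SAP 6.1.5 says "Prior medications are those which have been identified to have been discontinued prior to the treatment start date", and sends partial dates to Appendix 1 to decide concomitance.

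**The concern.** Conservative imputation resolves uncertainty towards treatment-emergent or concomitant. In these records the relevant point is not uncertain. If the reported end month is over before the dosing month begins, the event or drug ended before the first dose, whatever its start. Appendix 1 already accepts that a known pre-dose end should beat an imputed start, but applies this only when the day is recorded.

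The word *complete* cannot comfortably be read more widely. The final medication rule separates complete from imputed dates, so a programmer will take the term literally. That final rule also makes the medication case worse, because a reported partial stop date is replaced by a wholly imputed one.

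TEAE incidence is the first-listed primary endpoint (Protocol 8.5.1, SAP 2). Pre-dose records of both kinds exist by design: adverse events are collected from consent (Protocol 6.2), and medications are recorded for the 30 days before the screening visit (Protocol 6.3). A drug wrongly tabulated as concomitant would also look like use during the period in which Protocol 5.9 restricts medication.

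**Working it through.** There is no plan figure to reproduce. The check applies Appendix 1 literally to example records.

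**Inputs.** First dose 15 July 2023 (assumed). Screening opens at most 28 days earlier (Protocol Appendices 1 and 2): 15 July − 28 days = 17 June. The medication window opens up to 30 days before that: 17 June − 30 days = 18 May. An end date reported as June 2023 is therefore possible for both record types. Its latest possible value, 30 June, is 15 days before dosing, so the drug example also respects the 14-day exclusion (Protocol 4.3, criterion 14).

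**Adverse events**

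| Reported start | Reported end | Start after Appendix 1 | Flag | Shown by the end date |
|---|---|---|---|---|
| missing | June 2023 | 15 July 2023 | TEAE | pre-dose (flag wrong) |
| 2023 | June 2023 | 15 July 2023 | TEAE | pre-dose (flag wrong) |
| June 2023 | June 2023 | 30 June 2023 | not TEAE | pre-dose (right) |
| missing | 28 June 2023 | 28 June 2023 | not TEAE | pre-dose (right) |

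In the first two rows the imputed date is study day 1 with no time, which SAP 6.4.1 counts as treatment-emergent.

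**Medications**

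| Reported start | Reported end | Dates after Appendix 1 | Class | Shown by the end date |
|---|---|---|---|---|
| missing | June 2023 | start 15 July; end 30 June, then raised to 15 July | concomitant | stopped pre-dose (class wrong) |
| 2023 | June 2023 | 1 January to 30 June | prior | stopped pre-dose (right) |
| June 2023 | June 2023 | 1 June to 30 June | prior | stopped pre-dose (right) |
| missing | 28 June 2023 | 28 June to 28 June | prior | stopped pre-dose (right) |

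**Conditions for the error.** For an adverse event: a start that is missing or year-only in the dosing year, and a partial end wholly before the dosing month. For a medication: a completely missing start and such an end. A year-only end in the previous year behaves the same way, but falls within the collection windows only for doses early in a year: up to 28 January for events (28 January − 28 days = 31 December) and up to 27 February for drugs (27 February − 58 days = 31 December, where 58 = 28 + 30).

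**Size.** An active cohort has 6 subjects. One misclassified event changes overall TEAE incidence from k/6 to (k + 1)/6, that is 1/6 = 16.7 percentage points, if the subject has no other TEAE. If the subject has one, the change is 0, because SAP 6.4.1 counts a subject once per category. The event count still rises by one, and a system organ class or preferred term row may rise by 1/6. Placebo subjects are pooled across cohorts (SAP 5.1), so their denominator differs.

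**With the override extended to partial end dates.** The wrong event rows become start 30 June, not TEAE. The wrong medication row becomes 30 June to 30 June, prior. With a missing start and an end of July 2023 or simply 2023, the latest possible end (31 July or 31 December) is after 15 July, so the start stays at 15 July and the record stays treatment-emergent or concomitant.

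**The case against.** The best counter-argument is that the rule hardly ever matters here. A record needs two incomplete dates at once. An adverse event must be new or worse since Screening (SAP 6.4.1), so a pre-dose onset is confined to about four weeks. Subjects are in the unit from Day -3, the investigator follows each event from onset, and Protocol 7 and 9.11 provide for data checks and clarification of entries with the site. A blank start beside a month-only end should be queried. The error over-counts, in line with the SAP's other defaults for missing severity and relationship. It also stays visible, since SAP 5.3 presents data as collected and all events and medications are listed by subject. On the drug side, SAP 6.1.5 also calls therapy ongoing at enrolment concomitant, so a drug stopped during screening could arguably fit both definitions.

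Most of this stands, and it settles the size: the point is minor. It does not rescue the rule. Rarity and listings limit the harm, but the flag still contradicts the record. Over-counting is a reasonable default only while the end could fall on or after dosing. The overlap in SAP 6.1.5 does not help either: a drug stopped before consent is prior on any reading, yet Appendix 1 makes it concomitant if its start is blank and its end is partial.

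**Conclusion.** The gap is real and narrow, and of minor severity. Every record meeting the conditions above is misclassified, and no other section lets a partial end date override the imputed start. How many such records will arise is not given. They are probably few, and more plausible for medications, where recall reaches back before screening. The 16.7 points is a maximum for one subject in a 6-subject active cohort, not an expected effect. The medication error changes a descriptive table and no endpoint.

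Two stronger readings should be resisted. A reader might infer that everything that ended in a month before dosing is misclassified; the tables show that most partial-date patterns are not. A reader might also infer that a wrong concomitant flag would create a protocol violation and remove a subject from the Per Protocol Set. The documents do not support this: deviations are identified and classified on the CRF before database lock (SAP 6.1.2), and Appendix 1 dates only set flags.

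The conclusion assumes that Appendix 1 is programmed as written and that such records survive data cleaning.

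**What to change.** In Appendix 1, replace the start-date override in both algorithms with wording such as: *If the imputed start date is later than the end date (as reported if complete, at its latest possible date if partial), the start date is set to that end date.* Define the latest possible date as the last day of the reported month, or 31 December of a year-only end; adverse event end dates have no such convention at present.

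State that this step comes before the final medication rule. A reported partial end is then never raised to a wholly imputed start, and the final rule needs no change of its own.

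The cost is a sentence or two in the SAP and the matching program lines. No new data are needed, and no event that could have begun on or after the first dose loses its flag.

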
07-Sep-2023 | 14:40 AEST

[figure not shown]
PK Section Author: [name]
Consultant Pharmacokineticist

Date

Part B (MAD) will evaluate up to 3 doses based on the doses established during Part A (SAD). Each subject in Cohorts 1 and 2 will receive study drug for 7 days, administered once daily. Subjects in Cohort 3 will receive study drug for 7 days, administered twice daily. All subjects in each Part B (MAD) cohort will have their AE, PK, and electroencephalography (EEG) data, acquired up to and including Day 8, evaluated for safety and tolerability by the CRC before opening the next higher dose cohort. Subjects will be housed in the clinic from Day -3 prior to study drug administration and will remain in-house for 24 hours post morning dose (Day 8) for PK and safety assessments.

The study will be comprised of 3 periods: Screening (up to 28 days); Treatment (1 day for Part A (SAD) subjects and 7 days for Part B (MAD) subjects); and Follow-up. Subjects will have a follow-up visit 7 days after the last dose. As SAD dosing is a single dose on Day 1, follow-up will occur on Day 7. Part B (MAD) Cohorts 1 and 2 dosing involves single daily dosing on Days 1 to 7, with a follow-up visit occurring on Day 14. Part B (MAD) Cohort 3 dosing involves twice daily dosing on Days 1 to 7, with a follow-up visit occurring on Day 14.

Figure 1. Study Phases and Activities

